#### **14.6 Future Use of Stored Specimens and Other Identifiable Data**

De-identified study ID and no protected health information (PHI) data will be included in the analytical dataset. Data will be stored within a secure folder on the research server with limited access to project team members for the required timeframe. This study does not involve genetic testing or collection of specimens.

## **15 DATA HANDLING AND RECORD KEEPING**

The investigators in the TMD Pain Study will be responsible for ensuring the accuracy, completeness, legibility, and timeliness of the data reported. Since most of the data collected will be through the secure PACT website, accuracy and completeness of the data is maximize through alerts and pop-ups if the data is inconsistent or not entered. All source documents will be completed in a neat, legible manner to ensure accurate interpretation of data. We will also maintain adequate case histories of study participants, including accurate case report forms (CRFs), and source documentation. See a comprehensive Data Management Plan located in the Manual of Operations and a Data Management and Safety and Monitoring Plan in **APPENDIX J** below.

### **15.1 Data Management Responsibilities**

Data collection and accurate documentation will be the responsibility of all TMD Self-Care Study staff under the supervision of the PI. A programmer from HPI will develop our initial contact tracking database using REDCap (Electronic Data Capture) software to track all phone calls, contacts, and information for participants. All source documents and assessment reports will be reviewed by the study team and data entry staff, who will ensure that they are accurate and complete. Unanticipated problems and adverse events will be reviewed by the investigator or designee.

### **15.2 Data Capture Methods**

Since assessment data is all entered electronically within the TMD Pain Study website, accuracy and completeness of the data is maximize through alerts and pop-ups if the data is inconsistent, out of range, or not entered. The database is centrally located with ongoing processing. The data entry procedures include a secure intra-net log-in that is password protected and data entry will have data quality checks with the electronic data system.

### **15.3 Types of Data**

Self-report assessment and outcome measure data that involve questionnaire responses are collected in the secure TMD Pain Study Website. Safety data are collected in a separate database related to each participant.

### **15.4 Schedule and Content of Reports**

Reports to monitor enrollment rate, will be generated each week by the data from REDCap Software and the TMD Pain Study website. These reports will be discussed at the weekly investigator meeting.

### **15.5 Study Records Retention**

Study records will be maintained for at least three years from the date that the grant federal financial report (FFR) is submitted to the NIH. No records will be destroyed without the written consent of the sponsor, if applicable. It is the responsibility of the sponsor to inform the investigator when these documents no longer need to be retained.

### **15.6 Protocol Deviations**

A protocol deviation is any noncompliance with the clinical study protocol, Good Clinical Practice, or Manual of Procedures requirements. The noncompliance may be on the part of the

participant, the investigator, or study staff. As a result of deviations, corrective actions that address the non-compliance issue have been developed by the study staff and will be implemented promptly. These practices are consistent with investigator and sponsor obligations in ICH E6:

- Compliance with Protocol, Sections 4.5.1, 4.5.2, 4.5.3, and 4.5.4.
- Quality Assurance and Quality Control, Section 5.1.1
- Noncompliance, Sections 5.20.1 and 5.20.2.

All deviations from the protocol will be addressed in study participant source documents and promptly reported to NIDCR and the local IRB, according to their requirements.

-

---

## 16 PUBLICATION/DATA SHARING POLICY

This study will comply with the [NIH Public Access Policy](#), which ensures that the public has access to the published results of NIH funded research. We will submit all final peer-reviewed journal manuscripts that arise from NIH funds to the digital archive [PubMed Central](#) upon acceptance for publication.

The International Committee of Medical Journal Editors (ICMJE) member journals have adopted a clinical trials registration policy as a condition for publication. The ICMJE defines a clinical trial as any research project that prospectively assigns human subjects to intervention or concurrent comparison or control groups to study the cause-and-effect relationship between a medical intervention and a health outcome. Medical interventions include drugs, surgical procedures, devices, behavioral treatments, process-of-care changes, and the like. Health outcomes include any biomedical or health-related measures obtained in patients or participants, including pharmacokinetic measures and adverse events.

The ICMJE policy requires that all clinical trials be registered in a public trials registry such as [ClinicalTrials.gov](#), which is sponsored by the National Library of Medicine. Other biomedical journals are considering adopting similar policies. For interventional clinical trials performed under NIDCR grants and cooperative agreements, it is the grantee's responsibility to register the trial in an acceptable registry, so the research results may be considered for publication in ICMJE member journals. The ICMJE does not review specific studies to determine whether registration is necessary; instead, the committee recommends that researchers who have questions about the need to register err on the side of registration or consult the editorial office of the journal in which they wish to publish. [U.S. Public Law 110-85](#) (Food and Drug Administration Amendments Act of 2007 or FDAAA), Title VIII, Section 801 mandates that a "responsible party" (i.e., the sponsor or designated principal investigator) register and report results of certain "applicable clinical trials:" *NIH grantees must take specific steps to ensure compliance with NIH implementation of FDAAA. These steps include;*

1. Determine if the competing application or funded grant supports an applicable clinical trial that is required under FDAAA to be registered in ClinicalTrials.gov
2. Include a certification of compliance in the competing grant application and progress report.
3. If the grant supports an applicable clinical trial, then determine which entity or individual is the responsible party
4. If the grantee is not the sponsor and therefore not the responsible party, contact the responsible party to ensure that the responsible party registers the trial and reports results as appropriate.
5. If the grantee is not the sponsor and therefore not the responsible party, contact the responsible party to ensure that the responsible party registers the trial and reports results as appropriate
6. The responsible party must regularly update information in the applicable clinical trial record.
7. If required, the responsible party must report summary results (including adverse event information) not later than 1 year after the trial completion date

### APPENDIX A: SCHEDULE OF EVENTS

Below is a schedule of events that include initial, intermediate, and final study visits, and all contacts with participants, e.g., telephone, website, screening, and other contacts includes the permissible time windows for study visits, For each visit, the purpose and description of what will occur at the visit.

Contacts with participant	Identification Phase	Telephone Screening Phase	Consent Phase	Intervention Phase	1 st Post-Intervention Phase	2 nd Post-intervention Phase	Interview Phase
Time Period (weeks)	Week 1 Pre-	Week 0 Pre-	Week 0 Pre-	Week 1-8 Intervention	Week 8 Post-	Week 16 Post-	Week 16 Post-
EMR List of TMD patients	X						
Demographics information	X	X					
Inclusion/ Exclusion Criteria		X					
Recruitment			X	X			
Consent/ HIPPA Form			X	X			
Baseline Questionnaire			X	X			
Intervention Compliance/ adherence				X			
Coach support				X			
Outcomes Compliance/ adherence					X	X	
8 week Questionnaire					X		
16 week Questionnaire						X	
Qualitative interviews							X
Adverse Event Reporting				X	X		

## APPENDIX B: PACT CONTENT AND TEXT FOR INTRODUCTORY VIDEO

**Description.** The PACT program is an innovative self-management training program of care that focuses on integrating robust self-management training with a health coach to engage, empower and educate participants to reduce risk factors and enhance protective factors for the condition. In 2011, the Institute of Medicine (IOM) stated that health professional’s primary role for chronic pain should be guiding, coaching, and assisting participants with day-to-day self-management of chronic pain and established research involving self-management as one of the highest priority topics.

To support self-management, the use of web-based on-line programs has been applied to train participants in self-management for many chronic conditions, but has not yet been applied to participants with pain conditions such as TMD. The use of on-line training with health coaches have distinct advantages that require minimal change in work-flow and time commitment of busy health professionals while making the innovative care model affordable, rapidly deployed, scalable, and transferable to other settings and conditions.

**A. Background to the PACT program.** Humans are complex, multi-dimensional, and dynamic beings and live within an ever-changing physical and social environment that contributes to the balance between health and illness. Yet, our traditional biomedical model is based on a scientific paradigm that is uni-dimensional, reductionistic, and inflexible that is based primarily on understanding the underlying pathophysiology. Health care professionals tend to see what they treat and treat what they see. If they see only the pathophysiology, they do not recognize and understand the complex risk and protective factors that interact and play a powerful role in the onset, perpetuation, and progression of any illness. As a result, success of treatment is often compromised by limited approaches that only address part of the problem. When treatment approaches are limited, outcomes are limited. This explains why systematic reviews of efficacy of nearly every biomedical treatment for chronic illnesses have shown that even with the most efficacious treatments, they improve outcomes by only slightly above placebo. Patients have more influence over the outcomes of their illness than any treatment provided by clinicians. Thus, when evidence-based biomedical treatments are combined with robust self-management training, they have transformed the patient from one of illness to health and wellness– thus, the development of a transformative care model. The clinical paradigms associated with the PACT program are described in Table 1. This is the basis for the PACT program and its 8 lessons.

New paradigm	Description and presenting concept
Understand the whole patient	We need to identify all diagnoses, risk factors, and protective factors in the 7 realms of life (body, mind, spirit, lifestyle, emotion, social, and physical environment) to shift the balance from illness to health.
Each patient is complex	There are usually multiple conditions and interrelated contributing factors may initiate, result from, increase risk, or decrease risk of illness. Each need to be addressed as part of comprehensive management strategy.
Self-responsibility is	You have more influence on the problem than any treatment

key to recovery	provided. Will you take ownership and control of the condition?
Self-care	You will need to make daily changes in order to improve your condition. Will you be willing to take the time to do this?
Education and training	We will teach you how to make these changes.
Long-term change	Change only occurs over time and it may take months for the changes to have a large impact on reducing pain and symptoms.
Strong provider-patient partnerships	We, as health professionals, will support you as you make the changes. We can be an agent to help you change.
Personal motivation	Will you be able to make the changes needed?
Social support	You may need help to make these changes.
Change process	Change will occur incrementally over time.
Fluctuation of progress	Expect ups and downs during the recovery process.

**B. Components of the PACT program.** The total commitment time by patient to participate in the PACT program is about 1 hour of on-line education per week and 1 hour of activity per day for healthy habits and calming practice. In addition, there are several PAUSES during the day to pay attention to what is happening without judging in each of the 7 realms: Body, Lifestyle, Mind, Emotion, Spirit, Social life, and Environment (Table 2). The program includes the following components;

- ***PACT with the Patient.*** All patients make a commitment to the program by signing a PACT agreement with the health professional and the health coach. This highlights the patient's responsibility in complying with the self-management.
- ***Personalized Risk and Protective Factor Assessment.*** A self-assessment of the condition and its contributing factors is administered online or on paper, at home or in the office. The results are reviewed by the HCC to provide a personalized action plan to engage the patient in self-management, lifestyle changes and shared decision-making.
- ***PACT On-line training.*** Based on the assessment, experiential lessons are generated to recommend exercises and lifestyle changes to improve the condition, reduce risk factors for delayed recovery, and enhance protective factors that encourage healing. The PACT program for pain conditions consists for 8 Lessons designed for an 8-week program. Each lesson includes about 4 to 5 ten-minute video sessions for a total of about 50 minutes per week. They start with a brief self-assessment to personalize the recommendations followed with recommended video sessions based on the risk factors present and protective factors that are weak. The program includes both print handouts on the content and experiential daily changes that are recommended. A diary is provided to track daily practice and achievement in goals. The lessons are focused on understanding the big picture of their condition, how it can be improved by the balance between risk and protective factors in a person's life.

- **Animated Characters.** On-line training programs need to be brief, to the point, and engaging to have participants maintain interest over the 8 weeks of the program. One of the important elements is the animated characters that present the content. In PACT, we

[figure not shown]
[name]

Action Annie

Barrier Bob

Calming Kate

have 4 diverse characters with distinct positive personalities that present the content. [name] is a distinguished professor, researcher, and pain specialist who presents the lessons but also tells stories of the many patients he has managed over the years. Action Annie is a perky plain-speaking trainer whose main job is to help the participant implement their action plan within their lifestyle. Calming Kate is an experienced health professional who teaches mindfulness-based stress reduction with a calm voice, enlightening dialogue, and guided imagery. Barrier Bob is a no-nonsense barrier buster who helps participants identify and change barriers that may be confronted on the way to changing a person's health and life.

- **TeleHealth Coach (THC).** THCs are well-trained and certified health professionals who review assessments and provide self-management training to patients to facilitate their knowledge and skills necessary for self-management of chronic conditions. The process incorporates the needs, goals and life experiences of the patients and is guided by evidence-based interventions for the target condition.
- **Reminders.** Reminders can be sent through on-line platform on an opt-in basis for participants to schedule health coach visits, track progress, identify adverse events, or personalize self-management protocols. Participants have the choice of electronic options such as email, social media, and phone messaging.
- **Outcomes Dashboard.** The PACT website will provide updates of participant's progress and change in assessments as part of the PACT program.
- **Action Plan.** The action plan that is generated for each patient includes 3 components: Healthy habits, daily PAUSEs, and calming practice. Healthy habits means taking dedicated time each day to work on enhancing protective factors in order to decrease risk factors. PAUSE now means taking a time-out pause to check-in on what you are doing right now in a non-judgmental way. This is essential to living a life that is in the present and mindful of each protective factor to enhance health and well-being. P-pause, A-assess, U-understand, S-Start fresh, and E-energize with protective actions to achieve a long now.
- **Calming practice** includes spending a few minutes each day doing a brief relaxation technique allows many benefits. These include meditation to calm the mind, relaxing the muscles and nerves, contemplation about your life, prayer to ask for help, and reflection

on how you will move forward.

- **Support team.** Having friend or family team member who can support you and encourage you along your journey will help you be successful. If you haven't already, you will get another chance to sign up a teammate before you start Lesson 2, or can add one at any time using the team of your dashboard.

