## 5.8 Administration of Intervention

Course material will be administered through an on-line website program. The focus will be on both didactic knowledge and interactive content. The use of a health coach is also integrated into the online intervention and will be conducted through telephone calls with study participants on a regular basis determined by the coach and participant at the start of

the intervention period (see Appendix D for Health Coach Phone Protocol).

*Health Coach.* The self-management program will also be supported by 3 three health coaches who have specialized training in health coaching with additional training in TMD and chronic pain. Health coaches are already employed within HealthPartners to engage patients with several chronic illnesses. Three of these trained coaches will provide the coaching services for the study. An agreement or pact with the participant is implemented by the health coach to ensure understanding of self-management program and the importance of each step. An initial phone call is held with the participant to ensure that they understand the basics on the self-management training program and how to use the information technology. Phone support is provided on a weekly basis to answer questions and encourage understanding and adherence to the self-management program. A minimum phone contact of 3 calls including the initial call, touch base call, and final call is required. If a participant is very engaged in the health coaching, a maximum phone contact will be two times per week for three months. The average length of calls is intended to be initial call of 30-60 min. as needed with follow-up calls of 30 min. Audio recordings of the telehealth visits will not be completed since the analysis of the coaching model itself is not the focus of study outcomes and it may interfere with coaching. Fidelity of the health coaching component of the PACT program will be assessed by review of the coaching logs, including the number of contacts and adherence to the coaching model with discussion of goals, barriers, understanding, and motivation. Discussions will be held with health coaches to assess their experience and how they perceive it contributes to the overall the PACT program.

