### **B. PACT Experimental Arm**

1. Participants randomized to the PACT care arm will be electronically directed to the PACT website landing page which explains each step of the process. Participants will complete the initial PACT assessment for each lesson. Based on the assessment, the PACT website will provide personalized training lessons for each participant.
2. Participants will also participate in weekly phone coach sessions.
3. Participants will complete each lesson on a weekly basis in order to focus on, understand, and implement the steps in each lesson. New material will only be made available to participants every 7 days.
  - a. If participants fail to complete a lesson, they will be prohibited from accessing all future materials until the missed lesson is completed, even if it takes more than one week.
  - b. Participants who fail to complete each lesson within a month will be called by the study coordinator to identify if problem exists and may result in study withdrawal.
4. Participant will also continue participate in usual care from their dentist such as a splint or anti-inflammatory medications as needed. Some patients may be under care of another healthcare provider such as a physical therapist.
5. Adverse events will be recorded through the website assessments.

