#### 8.1.3 *Serious Adverse Events*

A **serious adverse event (SAE)** is generally defined as any untoward medical occurrence that results in death, is life threatening, requires inpatient hospitalization or prolongation of existing hospitalization, results in persistent or significant disability/incapacity, or is a congenital anomaly.

The study intervention is a patient-centered self-management program for TMD pain. Potential participants with serious medical or psychiatric conditions are excluded from the study at initial screening. If study participants develop an increase in pain or other health concerns during the course of the study whether or not related to the study intervention would be considered an adverse event. The PACT program is a web-based, tailored 8-week program supported by a health coach to help enhance understanding, compliance, and success in self-management for TMD pain. There are self-report assessments at the end of each week throughout the entire program to monitor progress, compliance, adverse events, risk factors, and protective factors. If study subjects develop an aggravation of the pain or a new symptom that the subject attributes to the study intervention this would be considered an adverse event. This will be monitored by both self-report within the PACT program weekly assessments as well as by the dental professional who is caring for the patient. Adverse events will be reported to the Study Coordinator, the PI and the PO.

If participants screen for depression, we will provide a list of mental health providers who they can consult with to ensure their safety.

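### Weekly adverse-event capture in PACT depends on continued use of the program, and the back-up contacts do not reliably reach a participant who stops logging in

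*Protocol*

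**What the plan says.** Three parts of the protocol govern routine collection in PACT.

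- **Where events are recorded.** Section 6.3 B: "Adverse events will be recorded through the website assessments". Section 8.1.3 gives the frequency: "There are self-report assessments at the end of each week throughout the entire program to monitor progress, compliance, adverse events". The same section names the treating dental professional as a second source.
- **What prompts the participant.** Appendix B, under the program components: "Reminders can be sent through on-line platform on an opt-in basis for participants to schedule health coach visits, track progress, identify adverse events".
- **What happens when a lesson is missed.** Section 6.3 B: "If participants fail to complete a lesson, they will be prohibited from accessing all future materials until the missed lesson is completed". The next step is a call: "Participants who fail to complete each lesson within a month will be called by the study coordinator to identify if problem exists".

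The control arm also records events through website assessments (Section 6.3 A), but Section 8.1.3 describes the weekly assessment only for the PACT program.

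**The concern.** Aggravated pain is the first risk listed in Section 2.3.1, and sustained increased pain is a listed ground for ending participation in Section 5.5. It is also a plausible reason for someone to stop using an exercise and self-management website without telling anyone. If the weekly question reaches only people who keep logging in, missingness of the safety data may be related to harm.

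Adverse effects are one of the grounds for stopping the study (Section 5.6; Appendix J, Stopping Rules), and the Annual Report must say whether event rates match pre-study assumptions (Section 11.3). Both judgements rest on the events recorded. Because the pilot exists to test methods for a multi-site trial, a weak collection route would carry forward.

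**Working it through.** The plan gives no figure for adverse-event capture, so there is none to reproduce. The check is to follow a PACT participant who stops logging in, still consents, and has not announced withdrawal, and to ask which contact would put an adverse-event question to that person.

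1. **Weekly website assessment** (6.3 B, 8.1.3). Needs a login, so it is lost. The prompt helps only those who opted in.
2. **Inquiry at each study visit** (8.4). Section 6.3 defines the visits in weeks 1 to 8 as website visits. A person who does not log in has no such visit.
3. **Coach calls** (5.8). "Phone support is provided on a weekly basis to answer questions and encourage understanding and adherence to the self-management program". The required minimum is three calls. The call content in Appendix D covers goals, barriers, program progress and the participant's own agenda; it lists no adverse-event question.
4. **Non-completion calls.** Section 6 has the project manager call if a phase is not completed within two weeks, to look for barriers; how this applies to a single lesson is unclear. Section 6.3 B has the coordinator call after a month, to look for a problem. Neither is specified as an adverse-event query.
5. **Contact at withdrawal or discontinuation** (5.5.2). Staff document the reasons, which is useful, but the withdrawal must first be recognised. For silent stopping that means going through step 4.
6. **Early Termination visit** (6.5). It repeats the final-visit procedures, but its timeframe is an unfilled placeholder. If consent is withdrawn, collection ends (5.5.1).
7. **Week-8 and week-16 evaluations** (6.4). These are for all participants, with weekly emails and up to three calls, and are said to include adverse-event questions. The follow-up surveys shown in Appendix G contain none. The website control flow in Appendix B prompts the surveys once the modules are completed. Appendix A marks adverse-event reporting in the intervention phase and at week 8, not at week 16.
8. **Dental professional** (8.1.3). No schedule or form for asking or reporting is given.

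Arithmetic for scale:

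- Share of weekly checks missed after stopping at the end of week k: (8 − k)/8. For k = 2, 6/8 = 75%.
- One-month trigger for the coordinator's call: about 4 of the 8 intervention weeks.
- If the 80% lesson-access target (3.2.1 b) is exactly met in an arm of 40 (11.2), 0.20 × 40 = 8 participants do not access every lesson. That is a ceiling on stoppers at the target, not a count of them: some will only be slow, and only 60% are expected to keep to the 8-week timeline (3.2.1 d).
- Worst case, with all event rates assumed: aggravated pain in 10% of 32 finishers gives 3.2 events; in 20% to 60% of 8 stoppers it gives 1.6 to 4.8. True rate: (3.2 + 1.6)/40 = 12% to (3.2 + 4.8)/40 = 20%. Recorded rate if no route captures any event among stoppers: 3.2/40 = 8%. This is a bound, not an estimate.

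**The case against.** The case against has force. Weekly coaching by phone does not depend on the website, the coordinator monitors online access each week (5.9) and is in frequent contact with the coaches (Section 8), and Sections 5.5.2 and 6.5 are aimed at people who leave. A participant in more pain may well say so on any of these calls. The week-8 and week-16 surveys also ask for current, worst and average pain, so worsening can be seen afterwards. That stands in part, but the items look back 30 days: a form completed on day 56 reaches back to day 26, so an aggravation that began and settled before then is not covered.

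Stronger readings are tempting, and the documents do not support them.

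- A reader might infer that the adverse-event assessment sits inside lessons that lock. No passage says so. The lesson assessment in Appendix B serves another purpose ("They start with a brief self-assessment to personalize the recommendations"), and Section 12 lists weekly pain and function assessments separately from module access. The lock blocks later material and leaves the missed lesson open. The gap comes from not logging in.
- A reader might infer that collection itself is opt-in. Only the reminder is.
- A reader might infer that people who stop because of pain are the least likely of all to be asked. The contacts above, some directed at exactly these people, rule that out as a stated fact.
- A reader might infer that the PACT event rate is biased downwards against control. The control arm also relies on the website, so the direction is not known.

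**Conclusion.** The point holds in this form: a PACT participant who stops logging in loses the only weekly adverse-event question the protocol specifies, and no contact outside the website is written so that it reliably asks one. Sections 6.4 and 8.4 promise such questions, but Appendix A, the Appendix B control flow and the Appendix G surveys do not deliver them consistently.

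The loss for one person follows from the week of stopping (75% of weekly checks after week 2). The number of people affected, the number of events lost and any difference between arms cannot be derived from the documents. The 8% against 12% to 20% holds only under assumed event rates and with every back-up failing. The conclusion also assumes that Appendix G shows the follow-up forms as they will be used. It should be corrected because the pilot tests methods for a larger trial and the remedy is cheap.

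**What to change.** 1. State in Sections 6.3 and 8.1.3 and in Appendix B that a short adverse-event and pain-worsening question goes to every randomised participant in both arms by calendar week in weeks 1 to 8, whatever the lesson progress and without opt-in. Opt-in can remain for scheduling and progress reminders.
2. Add the adverse-event item to the week-8 and week-16 forms in Appendix G, and send both by calendar date rather than on completion of the modules.
3. Reconcile Section 6.4, Appendix A and the Appendix B control flow so that all three show adverse-event questions at weeks 8 and 16 for everyone.
4. Report the percent of checks answered, by arm, alongside the event counts. The SAP lists no adverse-event summary at present, so this needs a line there.

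The cost is an automated message, one form item and edits to a few sections. The downsides are slightly more contact, including with control participants in a trial that measures adherence and retention, and more events to review, since Section 8.1.3 counts any increase in pain as an adverse event and Section 8.3.1 requires relatedness to be assessed for each.
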